Title of Study: MOBI: A Phase 4, Open-Label Study to Assess Effects of Mitigation Treatments on Bruising of CCH-Aaes Treatment of Buttock Cellulite in Adult Females

Lead Principal Investigator: Not applicable

Phase of development: 4

Objectives and Endpoints:	
Primary Objective	Primary Endpoint
To assess the effect of mitigation treatments on bruising in the buttocks of subjects with cellulite after the first treatment of QWO (CCH-aaes).	• The proportion of subjects by buttock at each level of bruising on the Investigator Assessment of Bruising Severity Scale, at Day 4, 3 days after QWO (CCH-aaes) injection. This 5-level scale ranges from 0 to 4, with 0 indicating no bruising or almost none, and 4 indicating very severe bruising.
Secondary Objectives	Secondary Endpoints
To assess investigator assessment of bruising with mitigation treatments in subjects with cellulite after the first treatment of QWO (CCH-aaes).	 The proportion of subjects for whom the investigator reported an improvement of bruising on the mitigation treated buttock on Days 4 and 7 as measured on the Investigator-Bruising Improvement Scale (I-BIS), a 3-point Likert scale, with a score on the higher end of the range indicating improvement with treatment. The proportion of subjects by buttock with bruising at each level of the Investigator Assessment of Bruising Severity Scale, by visit. This 5-level scale ranges from 0 to 4, with 0 indicating no bruising or almost none, and 4 indicating very severe bruising.
To assess subject assessment of bruising with mitigation treatments in subjects with cellulite after the first treatment of QWO (CCH- aaes).	 The proportion of subjects treated with QWO (CCH-aaes) reporting an improvement of bruising on the mitigation treated buttock on Days 4 and 7 as measured on the Subject-Bruising Improvement Scale (S-BIS), a 3-point Likert scale, with a score on the higher end of the range indicating improvement of bruising with treatment. The proportion of subjects by buttock bothered by the appearance of bruising on each buttocks on the Patient Bother by Bruising Scale, a 4-point scale, with a score of 1 indicating, extremely bothered.

Name of Sponsor/Company: Endo Pharmaceuticals Inc.

Name of Marketed Product: QWOTM(CCH-aaes)

Name of Active Ingredient: Collagenase clostridium histolyticum (CCH)

Secondary Objectives	Secondary Endpoints						
To assess the level of aesthetic improvement of cellulite after treatment of QWO (CCH-aaes) with and/or without bruising mitigation treatment.	• The proportion of subjects with an improved (+1 or better) score on the Investigator-Global Aesthetic Improvement Scale (I-GAIS) for either buttock at the Day 71 Visit compared to Baseline. The I-GAIS is a 7-level scale ranging from +3 (very much improved) to -3 (very much worse).						
To assess the safety of QWO (CCH-aaes) with mitigation treatment in subjects with cellulite.	• Percentage of subjects reporting each adverse event (AE) and treatment emergent adverse event (TEAEs).						
Exploratory Objective	Exploratory Endpoint						

Overall Design:

This is a Phase 4, multicenter, open-label, multiple dose study to assess the effect of mitigation treatments on injection site bruising and safety in adult women with moderate cellulite in the buttocks treated with QWO (CCH-aaes). Approximately 75 subjects will be screened in order to enroll approximately 48 subjects in 6 cohorts.

At the Screening Visit, subjects who meet all inclusion criteria and have no exclusion criteria according to the investigator's assessment will be assigned to 1 of 6 treatment cohorts. Subjects will be allocated to cohorts using a site specific Mitigation Treatment Assignment Table provided by the sponsor.

Pending site capabilities and available mitigation treatments, each site will administer each mitigation treatment, with approximately 1-3 subjects assigned to each mitigation treatment as shown in Table 1. Mitigation treatments will be administered at or after the initial treatment session of QWO (CCH-aaes).

Name of S	ponso	or/Company: End	lo Pharmaceuticals	Inc.				
Name of M	Iarke	ted Product: QW	O TM (CCH-aaes)					
Name of A	ctive	Ingredient: Colla	agenase clostridium	histolyticum (C	CCH)			
Table 1: Distribution of Mitigation Treatments								
QWO (CCH-aaes) ^a Mitigation Treatment					reatment			
	Ν	Left Buttock	Right Buttock	Left Buttock	Right Buttock			
Cohort 1	8	Up to 0.84 mg	Up to 0.84 mg		None			
Cohort 2	8	Up to 0.84 mg	Up to 0.84 mg	Co	ompression garment			
Cohort 3	8	Up to 0.84 mg	Up to 0.84 mg	None	Instant cold packs			
Cohort 4	8	Up to 0.84 mg	Up to 0.84 mg	None	Arnica patches			
Cohort 5	8	Up to 0.84 mg	Up to 0.84 mg	None INhance Post-Injection				
					Serum with TriHex			
					Technology			
Cohort 6	8	Up to 0.84 mg	Up to 0.84 mg	None	PDL treatment ^b			

^{a.} For each subject, an identical dose and injection count of QWO (CCH-aaes) should be administered for the first treatment session to each buttock. The number of injections may differ among subjects.

^{b.} Pulse dye laser (PDL) may be used at the settings selected according to the investigator's discretion.

Eligible subjects will receive up to 0.84 mg of QWO (CCH-aaes) per buttock in both buttocks for a total dose of 1.68 mg per treatment session for 3 treatment sessions (Day 1, Day 21 ± 3 days, and Day 43 ± 3 days). To reduce variance in the bruising observed on the left and right buttocks after the first treatment session of QWO (CCH-aaes), each buttock should be treated with the same number of QWO (CCH-aaes) injections on Day 1, of up to 12 injections per buttock. The number of injections may differ between treatment sessions; 12 injections per buttock may be administered during the first treatment session followed by fewer injections per buttock during the second and third treatment sessions.

Subjects will return to the site approximately on Days 2, 4, 7, and 14 (ie, 1, 3, 6, and 13 days after injection on Day 1) for additional evaluations and digital photography obtained with standardized parameters. After the first mitigation treatment session, on Days 4 and 7, the effect of mitigation treatments on the severity of bruising will be assessed using the I-BIS and the Investigator Assessment of Bruising Severity Scale. The effect of mitigation treatments on the severity of bruising will be assessed by subjects on the S-BIS and the Patient Bother by Bruising Scale. Safety will be assessed throughout the study by collecting AEs, and TEAEs, and assessing injection site reactions in the buttocks.

At the investigator's discretion, for the second and third QWO (CCH-aaes) treatment sessions on Days 22 and 43, subjects will be permitted to receive the same mitigation treatment to the right buttock as received during the first QWO (CCH-aaes) treatment session. The severity of bruising will be assessed at each visit. Subject and investigator assessments of satisfaction, aesthetic improvement, and digital photography will also be conducted on Days 22 (\pm 3 days) and 43 (\pm 3 days). Subjects will return to the site for last study visit on Day 71 for additional investigator assessments of bruising and digital photography.

Disclosure Statement: This is an interventional open-label, post-marketing study to evaluate the effect of mitigation treatments on the bruising induced by QWO (CCH-aaes). The efficacy of the mitigation treatments in reducing bruising and the safety of QWO (CCH-aaes) with mitigation treatments will also be assessed.

Name of Sponsor/Company: Endo Pharmaceuticals Inc.

Name of Marketed Product: QWOTM(CCH-aaes)

Name of Active Ingredient: Collagenase clostridium histolyticum (CCH)

Number of Subjects (planned): A maximum of 75 adult female subjects will be screened in order to enroll 48 adult female subjects into 6 cohorts, such that approximately 45 evaluable subjects complete the study.

Treatment Groups and Duration:

It is intended to enroll 6 treatment cohorts of 8 subjects each. Cohort 1, will receive QWO (CCH-aaes) and no mitigation treatment. Cohorts 2-6 will receive QWO (CCH-aaes) with different mitigation treatments.

Subjects will complete the study on Day 71. The expected duration of subject participation is up to 92 days.

Data Monitoring Committee: No data monitoring committee will be used for this study.

1.2. Study Schema

BID = twice daily, ET= early termination, rt =right, QID = 4 times daily

1.3. Schedule of Assessments

	Screening Period	Treatment Period							Follow-up Period
Procedures	Day -14	Day 1 (Baseline)	Day 2	Day 4	Day 7	Day 14	Day 22 (±3d)	Day 43 (±3d)	Day 71//ET (+ 7d)
Informed consent	X								
Inclusion/Exclusion criteria	Х								
Medical history/surgical history/cellulite history including previous treatments	Х								
Prior/Concomitant medications/procedures (including all prior medications/procedures for cellulite)	X	x	x	х	x	x	x	х	х
Physical examination (including height)	Х								
Weight	Х								Х
Fitzpatrick skin type	Xa								
Vital signs	Х	Xp							
Digital photography ^c		Х	Х	Х	Х	Х	Xd	Xd	Х
Cohort assignment	Xe								
QWO (CCH-aaes) administration		Х					Х	Х	
Subject Assessments									
Subject-Bruising Improvement Scale (S-BIS)			x	х	х	х	Xď		
Patient Bother by Bruising Scale ⁹				Х	Х		Xd		
Investigator Assessments				•	•	•			
Hexsel Cellulite Severity Scale (CSS) Subsection D	Xh								
Clinician Reported Photonumeric Cellulite Severity Scale (CR-PCSS)	Xi								
Selection and marking of dimples to be treated within both buttocks		Xc					Xd	Xq	
Investigator Assessment of Bruising Severity Scale		x	х	х	х	х	Xq		
Investigator- Bruising Improvement Scale (I-BIS) ^j			Х	Х	х	Х	Xď		

	Screening Period		Treatment Period						Follow-up Period
Procedures	Day -14	Day 1 (Baseline)	Day 2	Day 4	Day 7	Day 14	Day 22 (±3d)	Day 43 (±3d)	Day 71//ET (+ 7d)
Investigator- Global Aesthetic Improvement Scale (I-GAIS)							Xď	Х	Х

	Screening Period			Treatm	ent Per	iod			Follow-up Period
Procedures	Day -14	Day 1 (Baseline)	Day 2	Day 4	Day 7	Day 14	Day 22 (±3d)	Day 43 (±3d)	Day 71//ET (+ 7d)
Mitigation Treatment Cohorts									
Compression garments			X ^{k,p}						
Instant cold packs to the right buttock only		X ^{I,p}							
Arnica patches (OcuMend [®]) to the right buttock only		X ^{m, p}							
INhance Post-Injection Serum with TriHex Technology [®] to the right buttock only			X ^{n,p}						
Pulse dye laser (PDL) treatment to the right buttock only			X ^{o,p}						
Injection site reactions/local tolerability in each buttock treated		х	Х	х	х	Х	х	х	Х
Adverse events (AEs)		Xq							

^a Subjects with a Fitzpatrick skin rating of I-III will be included.

^b Before injection and approximately 30 minutes after injection. Pulse and blood pressure should be collected after the subject has been sitting for 5 minutes.

^c Buttocks will be photographed before and after injection site and dimple marking on Days 1, 22, and 43. Buttocks will also be photographed during the Days 2, 4, 7, 14, and 71 visits (ET) (no dimple or injection site markings).

^{d.} Before injection.

^e Subjects will be assigned to 1 of 6 cohorts according to a site specific Mitigation Treatment Assignment Table. Cohort 1 =no mitigation treatment; Cohorts 2-6 = mitigation treatments

^f. Before QWO (CCH-aaes) injection, and 5 and 15 minutes after injection.

^g Using mirrors, or photographs captured either by the subject or another person with the subject's imaging device (ie, cell phone, digital camera), or images captured by the investigator or designee using the site's digital photography system.

^h Baseline Hexsel CSS Subsection D must be '0' (absence of flaccidity or sagging skin) or '1' (slightly draped appearance) on each buttock.

ⁱ Baseline CR-PCSS rating must be a '3' (moderate) on each buttock.

^j Based on live assessments while the subject is in front of the investigator.

^k Compression garments will be worn after QWO (CCH-aaes) injection on Day 1 and worn 24 hours a day for the next 7 days.

Apply instant cold packs immediately after QWO (CCH-aaes) injection for 5-10 minutes immediately after CCH-aaes injection while subject is in a prone position.

^m Arnica patches applied BID for 2 days immediately after QWO (CCH-aaes) injection on Day 1.

- ⁿ Inhance Post-Injection Serum is applied QID directly on and around the injections site for up to 7 days after QWO (CCH-aaes) injection on Day 1, until resolution of bruising.
- PDL treatment between Days 1 (same day of QWO [CCH-aaes) injection) and Day 7 after QWO (CCH-aaes) treatment. PDL settings are according to the investigator's discretion.
- P For the second and third QWO (CCH-aaes) treatment sessions, at the investigator's discretion, subjects will be allowed to use the same mitigation treatment in the same buttock (as applicable) that received mitigation treatment for the first CCH-aaes treatment session.
- ^q AEs will be collected from the time the subject signed the ICF until end of the study or early termination.
- BID = twice daily, d = Days, ET = early termination, ICF = informed consent form, QID = Four times daily

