2.1. Background

The results of the pivotal studies (Studies EN3835-302 and -303) of QWO (CCH-aaes) in edematous fibrosclerotic panniculopathy, otherwise known as cellulite, supported FDA approval of QWO (CCH-aaes) for the treatment of moderate to severe cellulite in the buttocks of adult women. The approved dose of QWO (CCH-aaes) is 0.84 mg per treatment area (buttock) per treatment area for up to 2 treatment areas per treatment session, administered at 3 treatment sessions, approximately 21 days apart. This dose was shown to be an effective treatment of cellulite based on improvement in the severity of cellulite as determined by the investigator and the subject. Overall, the safety profile indicated that QWO (CCH-aaes) was well-tolerated (QWO Prescribing Information). Bruising (injection site bruising) was the most common AE (84%) in the Phase 3 studies. Bruising after the first treatment session was the most robust of the 3 treatment session, with the incidence, duration and severity of bruising decreasing with each subsequent treatment session (Endo Clinical Study Reports EN3835-202, EN3835-205, EN3835-302, EN3835-303).

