2.11. Adverse Events

Adverse Events (AEs), including both observed or volunteered problems, complaints, signs or symptoms must be recorded, regardless of whether associated with the use of study treatment. Study treatment includes QWO (CCH-aaes) and mitigation treatments.

The following information will be collected for all AEs:

- Verbatim description
- Injection Site Reaction (Yes/No)
- Date of Onset

- Date of Resolution/or Ongoing
- Severity (Mild, Moderate, Severe)
- Relationship to QWO (CCH-aaes) (Not Related, Unlikely Related, Possibly Related, Probably Related)
- Action taken with QWO (CCH-aaes) (None, Interrupted, Withdrawn)
- Relationship to Mitigation Treatment (Not Related, Unlikely Related, Possibly Related, Probably Related)
- Action taken with Mitigation Treatment (None, Interrupted, Withdrawn)
- Outcome (Recovered/Resolved, Recovered/Resolved w/Sequelae, Recovering/ Resolving, Not Recovered/Not Resolved, Fatal, Unknown)
- Whether or not a concomitant medication or procedure was required
- Classified as a serious adverse event (SAE) or not
- SAE Code (Death, Life-threatening, Inpatient or prolonged hospitalization, Persistent or significant disability/incapacity, Congenital anomaly or birth defect, Other medically important event)

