5. STATISTICAL METHODS

5.1. Overview

The primary efficacy endpoint will be summarized as frequency counts and percentages based on the Evaluable Population by cohort. Mean and standard deviation (SD) will also be provided.

The secondary and supportive efficacy endpoints except for change from baseline measures will be summarized as frequency counts and percentages based on the Evaluable Population by cohort and by buttock, where appropriate. The change from baseline measures will be summarized using descriptive statistics (n, mean, SD, median, minimum and maximum).

TEAEs will be summarized as frequency counts and percentages by preferred term and by cohort. The results and change from baseline for vital signs will be summarized using descriptive statistics.

Subject listings of all data from the eCRFs as well as any derived variables will be presented.

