5.7.1.2. Mitigation

The following information regarding mitigation treatments will be summarized for the treated buttock(s), by cohort:

• Number of mitigation treatment sessions per subject per QWO treatment cycle

• For subjects who had mitigation treatment done, the type of mitigation treatment received, by treatment visit

Note that for Cohort 2, mitigation treatment was administered to both left and right buttocks. For Cohorts 3-6, mitigation treatment was administered to right buttock only. Cohort 1 did not receive mitigation treatment and therefore will not be included in mitigation treatment summaries.

A subject listing containing mitigation treatment administration information will be provided.

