5.8.1.1. Adverse Event Conventions

The following conventions will be followed:

- Table by preferred term If an AE preferred term occurred multiple times within a body system for the same subject, the preferred term will only be counted once for the subject for the summary of preferred terms. If an AE body system occurred multiple times for the same subject, the body system will only be counted once for the subject for the summary of body systems. If a subject has any AE, the subject will be counted once in the summary of subjects with at least 1 AE.
- Table by preferred term and severity If an AE preferred term occurred multiple times within a body system for the same subject, only the most severe one will be used. If the most severe preferred term of an AE occurred multiple times within a body system for the same subject, only 1 will be counted. In addition, this summary will also contain the total number of subjects with at least 1 mild, 1 moderate, or 1 severe. If a subject has at least 1 severe AE, then the subject will be counted in the severe category. If the subject has no severe AEs, but at least 1 moderate AE, then the subject will be counted in the moderate category, and if the subject has no severe and no moderate AEs, but has at least 1 mild AE, then the subject will be counted in the mild category.
- Table of frequency of preferred terms Preferred terms will be ordered by their descending frequency within the treatment cohort. If 2 or more preferred terms are tied in their frequency, then the preferred terms will be ordered alphabetically.

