XXXX-XXXX	Cohort 2	Day 22	yyyy-mm-dd	No (xxxxxxxxx)		
		Day 43	yyyy-mm-dd	XXXX	Left Buttock	*****
					Right Buttock	Xxxxxxxx
		Day 71	yyyy-mm-dd	XXXX	Left Buttock	XXXXXXXXX

Listing 16.2.6.5 Patient Bother by Bruising Assessment All Enrolled Subjects

[1] Cohort 1 = No mitigation treatment; Cohort 2 = Compression garment on both buttocks; Cohort 3 = Instant cold packs on right buttock only; Cohort 4 = Arnica patches on right buttock only; Cohort 5 = INhance post-injection serum with TreHex technology on right buttock only; Cohort 6 = pulse dye laser treatment on right buttock only.

[2] Patient bothered by bruising rating was based on the following scale: 1 (Not at all bothered), 2 (A little bothered), 3 (Moderately bothered), 4 (Extremely bothered).

Datasets (extraction): status(ddmmmyyyy),

Source: ...\xxxxxxx.sas

ddmmmmyyyy:HHMM

Listing 16.2.6.7 Digital Photography All Enrolled Subjects

Subject ID	Cohort [1]	Visit	Assessment Date	Timepoint [2]	Photos Taken? If no, Reason
XXXX-XXXX	Cohort 1	Day 1	yyyy-mm-dd	Before marking dimples and injection sites	Yes
		Day 2	yyyy-mm-dd	N/A	Yes
XXXX-XXXX	Cohort 2	Day 1 Day 2	yyyy-mm-dd yyyy-mm-dd	xxxxxxxxxxx xxxxxxxxxxxx	No (xxxxxxxxx) xxxx

[1] Cohort 1 = No mitigation treatment; Cohort 2 = Compression garment on both buttocks; Cohort 3 = Instant cold packs on right buttock only; Cohort 4 = Arnica patches on right buttock only; Cohort 5 = INhance post-injection serum with TreHex technology on right buttock only; Cohort 6 = pulse dye laser treatment on right buttock only.

Source: ...\xxxxxxx.sas

L	isting 16	5.2.7.1
	Adverse E	lvents
All	Enrolled	Subjects

Subject ID	Cohort [1]	S: System Organ Class P: Preferred Term V: Verbatim [2]	Start Date (Study Day)/ Stop Date (Study Day)/ Duration [3]	T: TEAE? I: Injection Site Reaction? S: SAE? [4]	S: Severity T: Treatment O: Outcome	Relation to QWO/ Action Taken	Relation to Mitigation Treatment/ Action Taken
XXXX-XXXX	Cohort 1	S: xxxxxxxxxxxxx P: xxxxxxxxxxxx V: xxxxxxxxxxxxxx	yyyy-mm-dd (-xx)/ yyyy-mm-dd (xx)/ xx	T: Yes I: No S: No	S: Mild T: None O: Recovered/ Resolved	Not Related/ Not Changed	Not Related/ Not Changed
		S: xxxxxxxxxxxxxx P: xxxxxxxxxxxx V: xxxxxxxxxxxxx	yyyy-mm-dd (xx)/ Ongoing	T: Yes I: No S: No	S: Moderate T: Medication O: Recovered/ Resolved	Probable/ Withdrawn	Not Related/ Not Changed

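### Local reactions are assessed in each buttock, but AEs are listed and tabulated without side, which dilutes mitigation effects in Cohorts 3-6 on reactions that QWO also causes

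*Protocol*

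**What the plan says.** - **Assessment.** The schedules in Protocol 1.3 and SAP Table 2 carry a row for "Injection site reactions/local tolerability in each buttock treated", marked at Days 1, 2, 4, 7, 14, 22, 43 and 71/ET.
- **AE record.** SAP 2.11 lists the information collected for all AEs. The item on local reactions is a flag, "Injection Site Reaction (Yes/No", with no left/right item beside it. Attribution is a separate field: "Relationship to Mitigation Treatment (Not Related, Unlikely Related, Possibly Related, Probably Related".
- **Summaries.** SAP 5.1 states: "TEAEs will be summarized as frequency counts and percentages by preferred term and by cohort". Under SAP 5.8.1.1, when a term recurs in a subject, "the preferred term will only be counted once for the subject for the summary of preferred terms". A left, a right and a bilateral reaction therefore give the same count.
- **Shells.** The AE table shells have one column per cohort. Listing 16.2.7.1 shows "I: Injection Site Reaction" as a flag and has no side column. The list of data listings contains none for local tolerability.
- **Which side is mitigated.** SAP 5.7.1.2: "For Cohorts 3-6, mitigation treatment was administered to right buttock only". Both buttocks receive QWO. SAP 5.7 uses the left buttock as the subject's own control for efficacy.
- **Where side is kept.** Injection counts, mitigation location, bruising severity, I-GAIS and patient bother are all recorded or reported by buttock.

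**The concern.** Safety of QWO with mitigation is a stated secondary objective. In Cohorts 3-6 each subject has one mitigated and one unmitigated buttock, and the plan uses that pairing for efficacy but not for local reactions. A subject with pain or swelling is counted once whichever side it is on, so the left buttock can hold the cohort rate up however the right one responds.

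The overlap in reaction types is real. Protocol 2.2 links swelling and pain to QWO bruising. Protocol 2.3 names redness and swelling among the reactions to topical arnica. For pulsed dye laser it names discomfort and edema, with redness and bruising at higher settings. Several of the reactions a reader would want to compare between sides are therefore ones that QWO produces on both.

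**Working it through.** **1. The plan's own figures.** Protocol 9.1 gives 6 cohorts of about 8 subjects: 6 × 8 = 48. No power, alpha or effect size is stated. The only background rate is in Protocol 2.1: "Bruising (injection site bruising) was the most common AE (84%) in the Phase 3 studies". This is read as a subject-level rate, since no per-buttock rate is given.

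**2. Model (assumed).** Let p be the per-side probability of a reaction and r the left-right correlation, which the documents do not give and which is varied from 0 to 1. Then P(neither side) = (1−p)² + r·p(1−p) = 1 − 0.84 = 0.16. Solving for p:
- r = 0: (1−p)² = 0.16, p = 0.600
- r = 0.5: (1−p)(1−0.5p) = 0.16, p = 0.745
- r = 1: 1−p = 0.16, p = 0.840

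**3. Full prevention on the right.** The right-side rate falls from p to 0. The subject-level rate becomes the left-side rate p.

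| r | True right-side fall | Planned cohort rate | Cohort fall |
|---|---|---|---|
| 0 | 60 points | 84% to 60% | 24 points |
| 0.5 | 74.5 points | 84% to 74.5% | 9.5 points |
| 1 | 84 points | 84% to 84% | 0 points |

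**4. Added harm under the same term.** Let the mitigation add an independent right-side risk h. The cohort rate rises by 0.16 × h: 2, 4 or 8 points for h = 12.5%, 25% or 50%. In 8 subjects that is 0.16, 0.32 or 0.64 of a subject. The right-side rate itself would rise by (1−p) × h: 0.4 × h = 5, 10 or 20 points at r = 0, and 0.16 × h = 2, 4 or 8 points at r = 1. When the sides are strongly correlated, a by-side count of presence alone thus adds little for harm, which is why severity by side matters.

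**5. Sensitivity: 84% read per buttock.** With both sides at 84%, the subject-level rate is 1 − 0.16² = 97.4% at r = 0 and 84% at r = 1. Full right-side prevention brings it to 84%, a fall of 13.4 to 0 points.

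**6. Event types QWO does not cause.** With a zero left-side rate, the cohort rate equals the right-side rate, so there is no dilution. The chance of at least one case in 8 is 1 − 0.875⁸ = 66% at 12.5% risk and 1 − 0.75⁸ = 90% at 25%.

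**7. What 8 subjects can show (illustrative two-sided alpha 0.05).** For full prevention, a cohort against Cohort 1 by the normal approximation has power Φ((0.24 − 1.96 × 0.2245)/0.2163) = 18% at r = 0, and 7% at r = 0.5. At r = 1 there is no difference to detect. An exact McNemar test on 8 pairs needs at least 6 discordant pairs, all left-only (2 × 0.5⁶ = 0.031). Its power is P(Bin(8, p) ≥ 6) = 32%, 67% and 88% at r = 0, 0.5 and 1. With half of right-side reactions prevented, power is about 3-8% between cohorts (r = 0 to 0.75) and 4-6% paired.

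**The case against.** A reader might infer that the plan hides any safety effect of mitigation. The documents do not support that, for four reasons.

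- **Attribution is recorded and tabulated.** Each AE carries its relationship to mitigation and the action taken with mitigation. SAP 5.8.1 plans mitigation-related AE tables overall, by preferred term, and by preferred term and severity. In Cohorts 3-6 a local event judged mitigation-related generally points to the right. This stands as partial cover for harms. It is an open-label judgement, and it cannot show a protective effect or a left-right contrast.
- **Bruising is already shown by side.** Severity is tabulated left and right through Day 22, bother is reported by buttock, and I-BIS and S-BIS compare the sides directly. This stands for session 1. The schedule and SAP 2.7.3 list no severity rating after the one before the Day 22 injection, although the design narrative speaks of rating at each visit. Mitigation may be repeated after sessions 2 and 3. Pain and swelling have no by-side summary at any time.
- **Some named harms are not diluted.** For blistering with arnica, crusting with laser and frostbite with prolonged cold, the documents give no QWO background rate. If QWO does not cause them, step 6 applies.
- **The endpoint is subject-level.** The safety endpoint is a percentage of subjects, and the SAP delivers it. The by-buttock table improves the answer to the objective; it does not repair a broken analysis.

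The eCRF is not among the documents. Local tolerability has its own schedule row and may have its own page. SAP 5.1 promises listings of all eCRF data, and the AE listing prints the verbatim term. Side may therefore be captured, but nothing in the text provided requires it, and tables of coded terms would not show it.

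**Conclusion.** The point holds for local reactions that QWO also causes: pain, swelling and similar terms throughout, and bruising after the last by-side rating before the Day 22 injection. For these, the planned cohort rates dilute a mitigation effect in either direction. Full right-side prevention, worth 60 to 84 points on that side, appears as a fall of 24 to 0 points. An added right-side risk of 12.5% to 50% appears as a rise of 2 to 8 points, less than one subject in 8.

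These sizes rest on reading 84% as a subject-level rate, on an assumed correlation from 0 to 1, on added harm being independent, and on bruising standing in for reactions whose background rates are not given. It would be too strong to say that the cohort rate must stay at 84% after full prevention. On the subject-level reading that is only the fully correlated extreme. The sample size is unaffected.

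**What to change.** 1. Record side (left, right, both, not applicable) for injection-site reactions if the eCRF does not already do so, and list the item in SAP 2.11.
2. Add one descriptive Safety Population table of injection-site reactions by preferred term, severity and buttock. For Cohorts 3-6, include the within-subject cross-tabulation of mitigated against unmitigated side.
3. Add side to Listing 16.2.7.1.

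The cost is at most one field, one table and one listing column. Side must be back-filled from source for reactions already recorded. With 8 subjects per cohort the table is descriptive only. If the eCRF already captures side, only the SAP entry, the table and the listing column remain.
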